9.4.3 ANALYSIS OF THE SECONDARY ENDPOINT(S)

Secondary Outcomes: Efficacy

Outcomes for all patients regardless of discharge location:

The association between number of outpatient visits to a physical therapy center and intervention group will be examined using Poisson regression. Discharge location (home, inpatient rehabilitation) will also

be included in the model. If the interaction between intervention group and discharge location is significant, then pairwise comparisons of intervention group within each discharge location will be examined within the Poisson regression model. If the Poisson model does not fit the data well, alternative methods for count data will be considered.

Outcomes for patients discharged to inpatient rehabilitation:

Number of inpatient days in a rehabilitation center

The association between number of inpatient days in a rehabilitation center and intervention group will be examined using Poisson regression. If the Poisson model does not fit the data well, alternative methods for count data will be considered.

Outcomes for patients randomized to the X4 brace with the Motion Intelligence platform:

The association between patient satisfaction with the X4 brace, as measured by the SUS scale, and discharge location (home, inpatient rehabilitation) will be examined using the two sided, two sample t-test. If the usual assumptions required for the t-test are not met, either a suitable transformation, or an appropriate nonparametric method will be used.

The association between number of days of compliance and discharge location will be examined using Poisson regression. If the Poisson model does not fit the data well, alternative methods for count data will be considered.

The association between number of days of adherence and discharge location will be examined using Poisson regression. If the Poisson model does not fit the data well, alternative methods for count data will be considered.

Other outcomes:

Provider satisfaction with the X4 brace, as measured by the SUS scale will be described by calculating summary statistics (median, 25th percentile, 75th percentile, minimum and maximum).

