6.3 MEASURES TO MINIMIZE BIAS: RANDOMIZATION AND BLINDING

Randomization:

Prior to randomization, patients will be stratified according to discharge location (home, inpatient rehabilitation). Within each stratum, patients will be randomly assigned in a 1:1 ratio to the X4 brace with the Motion Intelligence platform or standard of care.

The Biostatistics Unit will develop a randomization procedure using a permuted block design within the REDCap system). Additional details of the procedure, including required record keeping, will be further developed upon approval of this protocol. The Biostatistics Unit has extensive experience in implementing and in producing detailed documentation for such procedures.

Blinding and Concealed Allocation

Due to the nature of the X4 brace, it is not possible to blind the investigators or the participants. The randomization assignment will be obtained from BRMS, after consent has been obtained, after it has been determined that the subject has met all inclusion/exclusion criteria, and after the discharge location has been determined.

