8 STUDY ASSESSMENTS AND PROCEDURES

8.1 EFFICACY ASSESSMENTS

Study Cohort Patients Only (Patients randomized to the X4 brace with the Motion Intelligence platform):

Patients will follow the prescribed exercises available on the patient application, with a number of the exercises actively tracked by the Mi360 sensor housed in the X4 brace. Compliance will be monitored by the physician and/or a delegated medical professional between postoperative visits on the Motion Intelligence dashboard.

Range of motion in flexion and extension will be measured twice daily within the patient application using the Mi360 sensor housed in the X4 brace. This information is then graphically presented on the home screen in the patient application over time. Range of motion can be tracked in real-time between postoperative visits by the physician and/or a delegated medical professional between postoperative visits on the Motion Intelligence dashboard.

Patient's will be required to access the application twice daily to enter their pain scores using the visual analog scale (0-10). Patient pain can be tracked in real-time by the physician and/or a delegated medical professional between postoperative visits on the Motion Intelligence dashboard.

All study patients:

All study patients will complete a daily "Daily Patient Log" starting the day after discharge from the hospital until postoperative day (POD) 56. This log will document the patient's location:

- Rehabilitation center or
- Home physical therapy or
- Physical therapy center
- Hospital (readmission)
- o Return to work (if applicable)

All study patients will be required to complete a preoperative and 8 week postoperative Knee Society Score questionnaire. This questionnaire is a standard of care for all total knee arthroplasty patients having surgery by Drs. [name] and [name].

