9.2 SAMPLE SIZE DETERMINATION

Sample Size Justification:

Based on preliminary data (from the Total Knee Arthroplasty Registry), there were 244 patients treated under the standard of care, with a KSS subjective score obtained between 6 and 10 weeks after surgery. We will use this information to estimate the KSS subjective score for the standard of care group at 8 weeks after surgery. The mean KSS subjective score in these patients was 108.5, with a standard deviation of 27.5. We believe that a 10 point improvement is clinically meaningful. We further assume that the scores for those discharged to home, and those discharged to inpatient rehabilitation will be similar, (i.e. no interaction between intervention group and discharge location). Therefore, we will use a two sided two-sample t-test to simplify the calculation. In addition, the KSS subjective scores in our preliminary data were normally distributed, and so the calculation uses the raw (untransformed) data.

A sample size of 120 patients per group will yield 80% power to detect a 10 point difference between the two intervention groups using a two sided two-sample t-test at the 0.05 significance level. As

dropout is expected to be very low, no adjustment for attrition will be made. Therefore, the total sample size will be 240 patients (120 per group).

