9.4.2 ANALYSIS OF THE PRIMARY EFFICACY ENDPOINT(S)

Statistical Methods:

Primary Outcomes: Efficacy

For each Knee Society Score, (objective score and subjective score), analysis of covariance (ANCOVA) will be used to examine the association between that score and intervention group (X4 brace, standard of care). The corresponding pre-op score will be included as a covariate in the model. Discharge location (home, inpatient rehabilitation) will also be included in the model. If the interaction between intervention group and discharge location is significant, then pairwise comparisons of intervention group within each discharge location will be examined within the ANCOVA model. If the usual assumptions of the ANCOVA model are not met, either a suitable transformation, or an appropriate nonparametric method will be used.

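### The outpatient physical-therapy visit model is valid but leaves out the pre-op Knee Society Scores; if these predict visits, some precision on this secondary endpoint may be lost.

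*Combined protocol and SAP*

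**What the plan says.** - **Visit model (9.4.3).** "The association between number of outpatient visits to a physical therapy center and intervention group will be examined using Poisson regression". Discharge location is added, with within-location comparisons if its interaction with intervention group is significant. No other baseline variable is named. If the Poisson fit is poor, unnamed count methods may be used instead.
- **Primary model (9.4.2).** Each 8-week KSS is analyzed by ANCOVA with discharge location, and "The corresponding pre-op score will be included as a covariate in the model".
- **Availability of the score (8.1).** "All study patients will be required to complete a preoperative and 8 week postoperative Knee Society Score questionnaire". Agreeing to the pre-op KSS is also inclusion criterion 7 (5.1). The Schedule of Activities (1.3) puts it before surgery and puts randomization between postoperative day 1 and discharge.
- **Randomization (6.3).** Within each discharge location, "patients will be randomly assigned in a 1:1 ratio".
- **Status of the endpoint (3 and 9.1).** Physical-therapy center visits are a secondary endpoint. They are one of two proxies for rehabilitation cost, and the only one listed for all patients. Inpatient days are analyzed only in those discharged to inpatient rehabilitation.

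**The concern.** A baseline measure that predicts the outcome can make a randomized comparison more precise at almost no cost. The pre-op KSS is required of everyone, is fixed before allocation and already serves in the primary analysis. It is plausible that preoperative knee function influences how much therapy a patient uses. If so, leaving it out keeps explainable variation in the visit comparison and leaves chance imbalance in baseline function uncorrected.

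What is at stake is limited to the precision of one secondary endpoint. That endpoint is nevertheless the only rehabilitation-use comparison planned across all 240 patients, and the sample size was not planned for it.

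**Working it through.** **1. The plan's own figure.** Section 9.2 states: "A sample size of 120 patients per group will yield 80% power to detect a 10 point difference between the two intervention groups". The calculation assumes a t-test, two-sided at 5%. The SD comes from "The mean KSS subjective score in these patients was 108.5, with a standard deviation of 27.5".

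n per group = 2 × (1.960 + 0.842)² × 27.5² / 10² = 118.7, so 119 by the normal approximation. The exact t-test gives 119.7, rounded up to 120. Power at 120 per group is 80.4% (normal) or 80.1% (t-test). The figure reproduces, but it concerns the subjective KSS. No mean, SD, dispersion or power is given for visits.

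**2. What adjustment could gain.** Let rho be the correlation between the pre-op score and the visit count. Variance with adjustment ≈ (1 − rho²) × variance without, and the equivalent sample size is 240 / (1 − rho²).

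| rho (assumed) | Variance reduction | Equivalent N |
|---|---|---|
| 0 | 0% | 240 |
| 0.1 | 1% | 242 |
| 0.2 | 4% | 250 |
| 0.3 | 9% | 264 |
| 0.5 | 25% | 320 |

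No value of rho can be taken from the documents.

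**3. Whether the planned standard error would show it.** In a plain Poisson model with equal arms, SE(log rate ratio) ≈ √(2 / (120 × mean visits)).

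- Mean 6: √(2/720) = 0.0527.
- Mean 12: √(2/1440) = 0.0373.

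This depends only on the total count, so a covariate cannot reduce it. The check was a simulation of 240 patients, 41% of them to inpatient rehabilitation (the share in 2.1), allocated 1:1 within location, with no treatment effect, 600 runs per scenario and one standardized covariate. Means of 6 and 12 and a gamma mixing variance of 0.25 are assumptions. For scale, the three sessions a week in 2.1 allow at most 3 × 8 = 24 visits. At mean 12 with overdispersion:

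| Correlation (absolute) | Plain SE, without → with covariate | Dispersion-scaled SE, without → with | Scaled ratio |
|---|---|---|---|
| 0.00 | 0.0373 → 0.0373 | 0.0743 → 0.0745 | 1.002 |
| 0.16 | 0.0373 → 0.0373 | 0.0754 → 0.0742 | 0.984 |
| 0.32 | 0.0372 → 0.0373 | 0.0796 → 0.0744 | 0.935 |
| 0.44 | 0.0373 → 0.0374 | 0.0863 → 0.0743 | 0.862 |

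The plain SE does not move. The true sampling SD does: at correlation 0.32 it fell from 0.0792 to 0.0749.

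A separate simulation with robust SEs (mean 12, coefficient of variation 0.7, rate ratio 0.80, all assumed) gave variance ratios of 1.000, 0.950, 0.901 and 0.800 when the covariate explained 0%, 5%, 10% and 20% of the variance. This agrees with step 2. The average log rate ratio was essentially unchanged by adjustment.

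**4. Overdispersion.** With the assumed extra variation, the plain Poisson test at a nominal 5% rejected a true null in 19% to 28% of runs at mean 6 and 34% to 38% at mean 12. Adding the covariate hardly changed this. Scaled SEs brought the rate to about 4% to 7%, except in the adjusted model at the strongest correlations (0.41 and 0.44). There it was 7.7% to 7.8% and the scaled SE was below the empirical SD (0.0743 against 0.0777 at mean 12).

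**The case against.** The strongest case against is that this is only an efficiency preference. It has five parts.

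- **No evidence that the score is prognostic.** The documents never link pre-op KSS to visits. Section 2.1 describes a fixed three-per-week schedule and a need for transport, so counts may depend mainly on when a patient moves to a center. This stands, and it is why the gain is given as a range that starts at zero.
- **The primary model is no precedent.** There, each score is adjusted for its own baseline; the pre-op KSS is not a baseline visit count. This stands. A reader might infer that 9.4.2 and 9.4.3 are inconsistent, but they are not.
- **The interval as planned would not narrow.** This is correct for the plain Poisson SE, so naming the covariates alone is not enough.
- **Adjustment might change the target.** With a log-link mean model and no interaction, the adjusted and unadjusted rate ratios estimate the same quantity. That assurance does not extend to every fallback: the logistic part of a zero-inflated or hurdle model is not collapsible. The fix therefore has to keep a log-link rate ratio.
- **Overdispersion matters more.** Under the assumptions in step 4 it does, and the covariate does not cure it. A dispersion-aware SE is needed in any case, and it is also what makes a gain from adjustment visible.

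None of this shows harm from adjusting: at zero correlation the SE ratio was 1.002.

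**Conclusion.** This is a modest efficiency improvement on a secondary endpoint, not a correction of an error. The planned model adjusts for the stratification factor and is valid under the planned randomization. If pre-op KSS predicts visits, adjusting for it reduces the variance by roughly rho squared: nil at rho 0, 1% to 4% at 0.1 to 0.2, 9% at 0.3. Gains near 25% need rho of about 0.5, and nothing in the documents supports a correlation of that size.

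Two stronger readings are tempting. A reader might infer that precision is certainly being lost; that requires a correlation the documents do not give. A reader might also infer that this is the trial's principal cost endpoint; the plan calls it secondary, one of two proxies, and does not rank them.

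The range assumes an approximately linear relation and an SE that reflects the actual dispersion. The simulations also rest on assumed visit means and extra-Poisson variation.

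**What to change.** In 9.4.3, before outcome data are seen:

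1. Name the pre-op subjective and pre-op objective KSS as covariates in the visit model, alongside intervention group and discharge location.
2. State that the treatment effect is a log-link rate ratio, reported with a robust or dispersion-scaled SE or from a negative binomial model, and choose one of these in advance. The result in step 4 at the strongest correlations favors a robust SE or the negative binomial model over simple scaling.
3. Impute any missing pre-op score with the overall baseline mean, ignoring arm, so that no randomized patient leaves the intention-to-treat set in 9.3.

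The cost is a few lines of text and one or two degrees of freedom (at most 240 − 3 = 237 down to 235 in the model without interaction). It needs no new data and no more patients. Timing matters because the trial is unblinded (6.3), and a covariate added later could look data-driven.

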2 INTRODUCTION

2.1 STUDY RATIONALE

Total Knee Arthroplasty (TKA) has become a rapid recovery surgery. Hospital stays are shorter with rehabilitation done either in an acute (AR), sub-acute (SAR) rehabilitation center, or at home. Therefore, the surgeon and the surgical team are only apprised of the patients' progress during routine postoperative office visits done at 2 and 8 weeks. This could potentially result in a delay of treatment for any complications related to surgery.

Following discharge from the hospital approximately 41% of TKA patients are transferred to an AR or SAR for further rehabilitation. The length of stay in these facilities varies greatly. The use of a monitoring device would allow the surgical team to remotely monitor the patient criteria for a safe discharge. This criteria includes ambulation of 150 feet, ability to climb stairs and the bending of the knee to 110 degrees. Therefore, the X4 brace could alert the surgical team of patients who are failing to progress as expected.

Home based programs require the patient perform prescribed exercise regimens twice a day. One regimen is done with the guidance of a physical therapist (PT). The second therapy is done by the patient without supervision. Though home based exercises are convenient, assuring patient compliance with these prescribed exercise regimens is unknown. Transition to an outpatient rehabilitation puts an added burden on the patient as most will require someone to drive them. Outpatient rehabilitation is 3 times per week leaving the remainder of the exercises up to the patient.

Patients and their care team need a solution to ensure both the compliance and accuracy with the exercise regimen. Currently, there is no method for the surgical team to ensure patients are following the protocols and progressing as expected. The surgical team needs a solution which would provide them more timely access to patient recovery status, activity and level of compliance. Additionally, the use of this device could also provide needed security for a patient as they are aware their surgical team is monitoring their recovery.

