3 OBJECTIVES AND ENDPOINTS

OBJECTIVES	ENDPOINTS	JUSTIFICATION FOR ENDPOINTS
Primary		
 To determine if patient postoperative outcomes, measured by the Knee Society Score, are improved by using the X4 brace with the Motion Intelligence platform To monitor the study group for any device related adverse events 	 To compare the Knee Society Scores, both objective and subjective scores, done preoperatively and at 8 weeks postoperatively between the control and study groups To monitor the study group for any device related adverse events 	The Knee Society Score is a validated tool used for assessing outcome in total arthroplasty patients Patients will be followed to ensure there are no issues with the utilization of the X4 brace
Secondary		
 To determine if there is a reduction in the rehabilitation costs (inpatient or outpatient) by using the X4 brace with the Motion Intelligence platform 	 To compare the number of inpatient days in a rehabilitation center between the control and study groups To compare the number of outpatient visits to a physical therapy center between the control and study groups 	To evaluate if the X4 brace provides user- friendly, cost-effective, enhanced patient recovery following total knee arthroplasty
 To evaluate patients satisfaction with the X4 brace with the Motion Intelligence platform 	 To evaluate patient's satisfaction with the X4 brace with the Motion Intelligence platform via the "System Usability Scale" (SUS) questionnaire (study group only) 	
 To evaluate patients compliance and adherence using the X4 brace with the Motion Intelligence platform 	• To measure patient's compliance using the X4 brace with the Motion Intelligence platform by counting how many days they used the platform as prescribed within an 8 week period. A patient will be	

OBJECTIVES	ENDPOINTS	JUSTIFICATION FOR
		ENDPOINTS
	considered compliant if they use the platform once a day.	
	 To measure patient's adherence using the X4 brace with the Motion Intelligence platform. Adherence is defined as performing the entire exercise routine as prescribed once a day. 	
 To evaluate provider satisfaction using the X4 brace with the Motion Intelligence platform 	 To evaluate provider satisfaction with the X4 brace with the Motion Intelligence platform via the "System Usability Scale" (SUS) questionnaire (study group only) 	In order for this technology to become part a postoperative regime the platform should be both effective and user friendly for the provider

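### Section 9.4.3 leaves the two rehabilitation-use counts on plain Poisson regression with an open-ended fallback; one variance-robust method should be named in advance.

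*Combined protocol and SAP*

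**What the plan says.** The Objectives and Endpoints table (section 3) sets the cost objective: "To determine if there is a reduction in the rehabilitation costs (inpatient or outpatient) by using the X4 brace with the Motion Intelligence platform". Two counts serve it, inpatient rehabilitation days and PT-center visits.

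Section 9.4.3 gives their analyses:

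- PT-center visits, all patients: "The association between number of outpatient visits to a physical therapy center and intervention group will be examined using Poisson regression". Discharge location is also in the model, and a significant interaction with intervention leads to comparisons within each location.
- Rehabilitation days, inpatient-rehabilitation stratum only: "The association between number of inpatient days in a rehabilitation center and intervention group will be examined using Poisson regression".

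Each is followed by the same sentence: "If the Poisson model does not fit the data well, alternative methods for count data will be considered". The section does not say how fit will be judged, which alternative will be used, or whether standard errors will be scaled or robust.

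On variability, section 2.1 says of rehabilitation centers: "The length of stay in these facilities varies greatly". On outpatient therapy it gives only a schedule: "Outpatient rehabilitation is 3 times per week leaving the remainder of the exercises up to the patient". No mean, standard deviation or dispersion is given for either count.

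**The concern.** Poisson regression takes the variance of a count to equal its mean. If the true variance is larger, the rate ratio is still estimated sensibly, but the model-based standard error is too small, the confidence interval too narrow and the p-value too low. A chance difference in rehabilitation use could then be reported as a saving. The same applies to the interaction test that decides whether visits are compared within each discharge location.

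The fallback does not settle the matter, because it is not a rule. Two analysts following section 9.4.3 could reach different methods from the same data, and those methods can have very different error rates. These are secondary endpoints, but they are the ones that carry the cost objective.

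The point concerns only the two between-arm counts. It does not concern the compliance and adherence day counts, which are compared by discharge location within the brace arm.

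**Working it through.** **Inputs from the documents.** The models and the fallback are in section 9.4.3. Section 2.1 gives the share going to inpatient rehabilitation: "Following discharge from the hospital approximately 41% of TKA patients are transferred to an AR or SAR for further rehabilitation". Applied to 240 patients, this is 0.41 × 240 ≈ 98, or about 49 per arm. PT visits use all patients, 120 per arm. The plan states no figure for the count endpoints, so there is none to reproduce.

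**Assumptions.** Two-sided 5% is stated only for the sample size (section 9.2, "using a two sided two-sample t-test at the 0.05 significance level") and is assumed here for the secondary tests. Every variance/mean ratio below is assumed.

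**Step 1: error if plain Poisson errors are kept.** With variance/mean ratio φ, the Poisson standard error is too small by a factor √φ, so

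type I error = 2 × [1 − Φ(1.96/√φ)].

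| φ (assumed) | 1.96/√φ | Type I error |
|---|---|---|
| 0.5 | 2.77 | 0.6% |
| 1 | 1.96 | 5.0% |
| 1.2 | 1.79 | 7.4% |
| 1.5 | 1.60 | 11.0% |
| 2 | 1.39 | 16.6% |
| 3 | 1.13 | 25.8% |
| 4 | 0.98 | 32.7% |
| 5 | 0.88 | 38.1% |

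Simulation (20,000 null trials per setting, negative binomial counts with assumed means 10 to 14, 49 or 120 per arm) agrees: 16.2–16.9% at φ = 2 and 37.7–38.8% at φ = 5.

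**Step 2: what φ means for rehabilitation stay.** At an assumed mean of 12 days, Poisson allows an SD of √12 = 3.5 days. An SD of √24 = 4.9 days gives φ = 2, and an SD of 6 days gives φ = 36/12 = 3.

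**Step 3: what φ could be for PT visits.** Suppose attenders make 6 to 18 visits, each whole number equally likely: mean 12, variance (13² − 1)/12 = 14. If a share p never attends, the mean is 12(1 − p) and the variance is (1 − p)(14 + 144p), so φ = (14 + 144p)/12 = 1.17 + 12p.

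| p (assumed) | φ | Type I error (step 1 formula) |
|---|---|---|
| 0 | 1.17 | 7% |
| 5% | 1.77 | 14% |
| 10% | 2.37 | 20% |
| 30% | 4.77 | 37% |

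For this pattern, nearly all the excess comes from the assumed non-attenders.

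**Step 4: error if the fallback is turned into a rule.** The simulation in step 1 also applied a Pearson goodness-of-fit test, with quasi-Poisson (scaled) errors when p < 0.05. At φ = 2 to 5 the test flagged misfit in at least 99.8% of trials with 49 per arm and essentially all with 120 per arm. Type I error was then 4.8–5.2%. At φ = 1.2 to 1.5 it was at most about 5.9%. Robust standard errors used throughout, without a small-sample correction, gave 5.2–5.7% at φ = 2 to 5.

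**Step 5: the alternatives are not interchangeable.** For the PT pattern in step 3 with 10–30% non-attenders, two separate simulations of a negative binomial Wald test gave type I error of 1.3% falling to 0.1%, and about 2% falling to 0.2%. Robust errors gave 5–7% in the same settings. Zeros mixed with a block of 6 to 18 visits do not follow a negative binomial distribution.

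**The case against.** The strongest reply is that the plan already provides for misfit. At the ratios where plain Poisson does real harm, a routine fit test would almost always detect the problem, and a switch to scaled errors would restore about 5% (step 4). Model fit can also be judged without looking at the treatment p-value. This stands as far as it goes: the 17–38% range describes a trial in which the fallback is not used. But the test and the scaled variance in step 4 were supplied for this check. Section 9.4.3 contains neither, and an unnamed alternative could as easily be the conservative one in step 5.

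The second reply is that the ratios are not taken from the documents. This also stands. A reader might infer that both counts are certain to be strongly overdispersed and that this trial therefore carries a 17–38% false-positive rate. The documents do not support that. Large variation is stated, without a number, only for rehabilitation stay. For PT visits there is only a thrice-weekly schedule, and without non-attenders the example in step 3 gives about 7%. Section 4.1 has the daily log record home therapy and PT-center therapy separately, so some patients with no center visits are plausible, but no share is stated. With a ratio below 1, Poisson would be conservative.

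A reader might also infer that the model would be chosen for its p-value. The documents do not say that. Section 6.3 says only that investigators and participants cannot be blinded. Nothing in section 9.4.3 says when, or by whom, fit will be judged.

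**Conclusion.** The concern holds as a matter of choosing and fixing the method. Plain Poisson is the first-line analysis for both cost-related counts, its errors are not protected against excess variance, and the fallback is neither defined nor binding. If plain Poisson were kept, type I error would run from 5% at a ratio of 1 to 38% at a ratio of 5, with 7% at 1.2 and 11% at 1.5. If misfit were checked and a scaled variance used, it would be about 5%. The documents do not show where in that range this trial lies. The figures rest on assumed variance/mean ratios and on an assumed two-sided 5% level for secondary tests. The primary analysis and the sample size are not affected.

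**What to change.** In section 9.4.3, state one method for both between-arm counts: a log-link Poisson model with robust (sandwich) standard errors and a small-sample correction. The correction matters most for rehabilitation days, with about 49 patients per arm. Use the same standard errors for the intervention-by-discharge-location interaction test on PT visits and for any within-location comparisons. Report the rate ratio with its 95% confidence interval. For these two counts, replace the fit-dependent sentence with a statement that any other count model, including negative binomial, is a sensitivity analysis only.

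The cost is one line in the plan and one software option, with no new data or patients. The estimate remains a rate ratio. The downside is that intervals will usually be wider than under plain Poisson, so a modest true reduction in rehabilitation use will be harder to declare significant.
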